2.1. Study Rationale

Study CVAC is designed to evaluate safety, tolerability, and PK of oral LY3526318 in healthy participants when LY3526318 is administered as a new formulation. In a prior Phase 1 study (CVAA), exposure did not increase beyond that observed at 100 mg, and the concomitant food administration reduced exposure compared to the fasted state.

In this limited SAD study, a crossover design was chosen to limit the variability of PK, especially for the comparison of PK after fed and fasted conditions. Given treatment-emergent adverse events (TEAEs) were mild in the previous SAD and MD (to 14 days) studies, participants should be able to safely tolerate a maximum of 4 single doses with 14 days of washout between dosing periods. Placebo doses are included to assess TEAEs and limit bias. Similarly, given that a Phase 1 study was previously conducted, sentinel dosing is not necessary. In addition, safety and PK will be assessed prior to each dose escalation to mitigate the possibility of more severe adverse events (AEs) and the PK exceeding the mean area under the concentration versus time curve (AUC) of the monkey NOAEL.

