9.4. Statistical Analyses

Statistical analysis of this study will be the responsibility of the sponsor and its designee.

Any change to the data analysis methods described in the protocol will require an amendment only if it changes a principal feature of the protocol. Any other change to the data analysis methods described in the protocol, and the justification for making the change, will be described in the statistical analysis plan and the clinical study report. Additional exploratory analyses of the data will be conducted as deemed appropriate. Study results may be pooled with the results of other studies for population PK analysis purposes.

The statistical analysis plan will be finalized prior to database lock, and it will include a more technical and detailed description of the statistical analyses described in this section. This section

is a summary of the planned statistical analyses of the most important endpoints, including primary and key secondary endpoints.

Pharmacokinetic analyses will be conducted on data from all participants who received a dose of LY3526318 and have evaluable PK.

Safety analyses will be conducted for all enrolled participants who received study intervention, whether or not they completed all protocol requirements.

For continuous variables, summary statistics will include the number of participants, mean, median, standard deviation, minimum, and maximum. Categorical endpoints will be summarized using number of participants, frequency, and percentages. Additional analyses of the data will be conducted as deemed appropriate and may be fully detailed in a statistical analysis plan.

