9.4.1. Safety Analyses

All study intervention and protocol procedure AEs will be listed, and if the frequency of events allows, safety data will be summarized using descriptive methodology. Summary statistics for AEs and SAEs will be provided by treatment arm and for all placebo participants combined.

Safety assessments include laboratory tests, vital signs, ECGs, and physical examination. The parameters will be listed and summarized using standard descriptive statistics. Additional analysis will be performed as required.

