6.0 Study Design

This is a Phase 1, randomized, double-blind and placebo-controlled single ascending dose (SAD, Part A) and multiple dose (MD, Part B) study of LY3526318 in healthy participants. A maximum of 16 participants (SAD and MD cohorts, size of 8) will be enrolled.

Part A (SAD):

A single cohort of 8 healthy participants will be randomized to a sequence in which LY3526318 or placebo will be administered in a 3:1 ratio. In each dosing period, different participants will receive placebo. In this adaptive dose study, subsequent dose levels will be selected based on safety and PK. Doses will be selected to maintain geometric mean $AUC_{0-\infty}$ below the lowest no-observed-adverse-effect level (NOAEL) from animal toxicology studies (154 μ g.h/mL).

Of the 4 treatment periods planned for Part A, up to 3 single dose levels will be assessed in a fasted state (fasting at least 8 hours prior to and at least 4 hours after dosing). Up to two of these dose levels that were assessed in a fasted state may also be assessed in a fed state (a high-fat meal or a light breakfast 30 minutes prior to dosing).

Randomized to Treatment/Sequence:

Treatment	SAD Periods [N=8]				
	Sequence [n]	A1 (f asted)	A2 (f asted)	A3 (f ed)	A4 (f ed)
1 [2]		P	L2	L3	L4
2 [2]		L1	P	L3	L4
3 [2]		L1	L2	P	L4
4 [2]		L1	L2	L3	P

Single doses are L1, L2, L3, L4, P (Placebo); L = level of dose (mg);

Abbreviations: N = number of participants; n = number of participants in specific population; SAD = single ascending dose.

Following a screening period of up to 28 days, eligible participants will be confined to the clinical research unit (CRU) from Day -1 until all study assessments are completed on Day 3. All participants will return to the CRU after the last study period for a final visit on Day 10.

Part B (MD):

After a dose is identified from Part A, multiple doses of LY3526318 or placebo will be administered for up to 5 days. Eight treatment-naïve participants will be randomized to receive LY3526318 or placebo in a 3:1 ratio. Additional participants will be enrolled for a total cohort size of 8 completers. Part B will involve dosing in a f asted or f ed state (e.g., standard meal or a light breakfast as described in site-specific manual) depending on the results from Part A. The dose regimen and fed/fasting will be selected with the intent not to exceed the AUC₀₋₂₄ achieved in Part A. Part B is not designed to assess the impact of food on exposure.

Randomized to Treatment/Sequence:

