6.2 Randomization

A randomization schedule will be prepared by the Biostatistics Department of PRA. Eight participants (numbered 101-108) will be assigned to one of the 4 sequences in Part A and 8 participants (numbered 201-208) will be assigned to Part B.

Replacement participants will receive the same randomization number as the participant to be replaced increased by 1000 and will be administered the same treatment (sequence).

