9.1.4 Pooling

Summary statistics will be calculated by study part, treatment (and time point, if applicable). Placebo data will be pooled for Part A (SAD). Placebo data from the periods under fed conditions (i.e. Periods 3 and 4 for Part A) will be reported as a separate treatment for each meal condition.

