17.1.1 Adverse Events

All AE summaries will include only treatment-emergent AEs. Treatment-emergent AEs (TEAE) are those which occur after the first dose of study drug. For the SAD part, TEAEs occurring following dosing in a specific period but before dosing in the next period will be attributed to that specific period.

A breakdown of the number of events, and the number and percentage of participants reporting each TEAE, categorized by system organ class (SOC) and preferred term (PT) coded according to the Medical Dictionary for Regulatory Activities (MedDRA) (version as per the Dictionary Coding Conventions), will be presented by treatment, overall active and overall for each study part, in descending order of total number of events by SOC and PT. One table is presented for all TEAEs and one table is presented for TEAEs considered to be related to the study medication. Participants will only be counted once within each SOC or PT per treatment.

Additionally, a summary table with TEAEs by severity and relationship to study drug will be presented by study part and treatment.

TEAEs of which the relationship to study drug will be classified as 'possibly', 'likely', or 'definitely' will be regarded as related, while TEAEs that are classified as 'none', or 'unlikely' will be regarded as not related in the tables

A listing of AEs leading to study discontinuation will be provided.

All AEs (including non-treatment-emergent events) recorded on the eCRF will be listed.

The following missing data will be imputed as defined (for calculations only/will not be presented):

- Missing AE start and/or end times for the calculation of onset and duration will be assumed to be at 00:01 for a start time and 23:59 for end times
- Missing AE severity or relationship will be assumed to be severe or related, respectively
- Missing AE start times for the determination of treatment emergence will be assumed to occur after treatment unless partial date documents the AE as happening prior to treatment
- Missing AE start times for the determination of treatment assignment will be assumed to occur after treatment on the recorded date one minute after dosing
- Missing AE start date will be assumed to be after treatment for the determination of TEAE and on treatment for single treatment studies but will not be attributed to treatment in studies with multiple treatments

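### Must the SAP add an all-placebo column to the adverse-event tables because the protocol asks for a combined placebo summary?

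*SAP*

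**What the plan says.** - **Protocol Section 9.4.1** states: "Summary statistics for AEs and SAEs will be provided by treatment arm and for all placebo participants combined". It sets a condition first: "if the frequency of events allows, safety data will be summarized using descriptive methodology". It names no study part.
- **SAP Section 17.1.1** says the tables of treatment-emergent events by system organ class and preferred term "will be presented by treatment, overall active and overall for each study part". The table by severity and relationship is planned by study part and treatment only.
- **SAP Section 9.2.2** lists three Part A placebo treatments (fasted, light breakfast, high fat) and one for Part B. SAP Section 9.5 makes these the table labels. The study-drug row of 9.2.2 has a plain placebo entry, but no AE table is tied to it.
- **SAP Section 9.1.4** first says Part A placebo is pooled, then that fed placebo is reported under its own label for each type of meal.
- **SAP Section 17.1.2 and Appendix 3** plan a participant listing of deaths and SAEs, and Table 12.3.1.1. No placebo grouping is stated.
- **SAP Section 7.1** declares no change from the protocol.

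**The concern.** Safety and tolerability is a secondary objective in both parts, and Protocol Section 2.1 gives the purpose of the placebo doses: "Placebo doses are included to assess TEAEs and limit bias". The protocol names the placebo summary it wants, and the SAP neither lists it nor records its absence. If the labels in 9.2.2 are followed literally, a pooled active column stands beside placebo columns of 4, 2 and 2 people. Percentages on two people can only be 0, 50 or 100, so a single placebo event looks very different from the same event in a group of eight. If the combined figure could not be recovered, the placebo reference would be weaker than the protocol promised, and a departure from the protocol would have gone undeclared.

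**Working it through.** **Inputs.** The sequence table in SAP Section 6.0 has four sequences of two people over four periods, with one placebo period per sequence. By SAP Section 9.2.2, Periods 1 and 2 are fasted, Period 3 follows a light breakfast and Period 4 a high-fat meal.

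**The plan's own figure.** In each period three sequences are active and one is placebo: 3 × 2 = 6 active and 1 × 2 = 2 placebo. This reproduces the stated 3:1 ratio.

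**Size of the placebo columns.**
- Fasted: 2 + 2 = 4
- Light breakfast: 2
- High fat: 2
- Total: 4 + 2 + 2 = 8

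**Overlap between columns.** SAP Section 6.0 says: "In each dosing period, different participants will receive placebo". No one is planned to be in two placebo columns, so the 8 are 8 distinct people. SAP Section 17.1.1 counts a person once per class or term within a treatment. Hence, for any term, combined placebo participants = fasted + light breakfast + high fat, with denominator 8. Event counts add in the same way.

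**Effect of the display.** One affected person gives:
- in the fasted column, 1/4 = 25%
- in either fed column, 1/2 = 50%
- in the combined group, 1/8 = 12.5%

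The percentages differ, but the count is 1 in each case. Counts should be added, not percentages, because SAP Section 9.1.1 rounds frequency percentages to integers.

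**Replacements.** Under SAP Section 6.2 a replacement follows the sequence of the person replaced. Each individual still has at most one placebo period, so the columns stay disjoint and the denominators still add, even if the total exceeds 8.

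**Study-wide reading of the protocol.** Section 9.4.1 is not limited to Part A. Part B has 2 placebo participants, all treatment-naïve, so a literal pool is 8 + 2 = 10 distinct people, and one event is 1/10 = 10%. This is again a sum of printed columns.

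**The two readings of SAP Section 9.1.4.**
- If only the fasted periods are pooled, the columns are 4, 2 and 2, which matches 9.2.2.
- If all Part A placebo is pooled and the fed groups are shown in addition, the column of 8 is already planned.

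Both readings give the same combined counts.

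**Why active differs.** There are 6 × 4 = 24 active participant-periods spread over 8 people, three each. The number of people with an event in any active period cannot be found by adding active columns, because the same person may appear in several. An overall active column therefore adds information that an overall placebo column would not. The overall column cannot stand in for placebo, since all 8 people also receive active drug.

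**The case for a change.** The best case for a change is procedural. The protocol names this summary. For changes of method that need no amendment, Protocol Section 9.4 says that they, with their justification, "will be described in the statistical analysis plan and the clinical study report". SAP Section 7.1 reports none, and SAP Section 9.5 provides no table shells that would settle the layout. One column and one clearer sentence would cost almost nothing.

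The textual mismatch stands, and a sentence stating what 9.1.4 pools would be tidier. The rest has less force. SAP Section 3.0 requires identification of substantial differences only, and a column that equals the sum of its neighbours is hardly that. The first sentence of 9.1.4 can be read as already authorising the pool. SAP Appendix 3 lets the medical writer add tables to the report outside the SAP, so a combined figure can be supplied without revising it. The meal split is not a departure either: Protocol Section 9.1 asks for summaries by dose and fed status.

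The SAE part of the objection is thin. The protocol makes safety summaries depend on event frequency, and the synopsis reports no SAEs in the previous study of this drug. A listing by participant shows every SAE among at most 16 planned people.

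It is also true that the overall active column covers three periods per person and each placebo column one. That is evident from the crossover, and each single active column (6 people, one period) offers the like-for-like comparison.

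**Conclusion.** No change is needed. This is a gap in wording that analysts can fill sensibly: the protocol asks for a combined placebo summary, and the SAP leaves unclear whether it will be printed. The combined Part A group is 8 people (10 if Part B is included), and its counts are the exact sum of the planned placebo columns. The visible effect is limited to percentages: 25% or 50% in a split column against 12.5% combined for one affected person. Neither document plans a test or a decision rule on placebo event percentages, and the primary pharmacokinetic endpoints are untouched.

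The conclusion assumes that participants receive their randomised sequence, so that nobody takes placebo in two Part A periods, and that the tables print participant counts as SAP Section 17.1.1 plans. A dosing error that broke the first assumption would show in the dosing listing and affect a single count.

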9.1.3 Descriptive Statistics

Unless otherwise indicated, continuous variables will be summarized with the following descriptive statistics: n (number of observations), (arithmetic) mean, standard deviation (SD), minimum value, median, and maximum value.

Categorical data will be summarized with frequencies and percentages. Percentages by categories will be based on the number of participants exposed within a treatment.

For categorical data the categories will be presented in the tables exactly as they appear in the eCRF/Database.

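### In the Part A TEAE tables the overall active column covers three dosings per participant and every placebo figure covers one, so the two percentages are not comparable

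*SAP*

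**What the plan says.** **Design.** Part A is "A single cohort of 8 healthy participants", "randomized to a sequence in which LY3526318 or placebo will be administered in a 3:1 ratio" (SAP 6.0). The same section adds: "In each dosing period, different participants will receive placebo". The sequence table there, and in protocol 1.2, gives each of four sequences (2 participants each) three active periods and one placebo period.

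**TEAE tables.** SAP 17.1.1 specifies "A breakdown of the number of events, and the number and percentage of participants reporting each TEAE", shown "presented by treatment, overall active and overall for each study part". In Appendix 3 these are Tables 12.3.1.4 (all TEAEs) and 12.3.1.5 (related TEAEs). The counting rule is: "Participants will only be counted once within each SOC or PT per treatment". In Part A an event belongs to the period running from one dosing to the next.

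**Denominator.** SAP 9.1.3: "Percentages by categories will be based on the number of participants exposed within a treatment".

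**Placebo.** SAP 9.1.4 and 9.2.2 show Part A placebo as three treatments: fasted, light breakfast and high fat. SAP 17.1.1 names no overall placebo column. Protocol 9.4.1 does plan one: "Summary statistics for AEs and SAEs will be provided by treatment arm and for all placebo participants combined".

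**The concern.** A percentage of participants with at least one event rises with the number of dosings over which each person is watched. The overall active column watches each Part A participant through three dosings, and each placebo column through one. Pooling placebo across meal conditions, as protocol 9.4.1 describes, brings its denominator to 8 but leaves one dosing per person. The SAP gives no participant-period denominator, rate or footnote.

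Overall active is the only pooled drug figure in these tables. Protocol 2.1 says placebo is there to help assess TEAEs and limit bias, and safety and tolerability is a Part A secondary objective. A reader who sets the pooled drug column beside placebo would expect to see an excess even if the drug did nothing.

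**Working it through.** **Inputs from the documents.** 4 sequences, 2 participants each, 4 periods; one placebo period per sequence (SAP 6.0). Periods 1 and 2 are fasted, Period 3 is light breakfast, Period 4 is high fat (SAP 9.2.2).

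**The plan's own ratio.**
- Dosings: 4 × 2 × 4 = 32.
- Active: 8 × 3 = 24. Placebo: 8 × 1 = 8. The ratio is 3:1, as stated.
- Each period has 6 participants on active and 2 on placebo. The planned placebo columns are therefore 4 (fasted), 2 (light breakfast) and 2 (high fat).

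**Assumptions.** The documents give no adverse-event rate and no within-person correlation. Let p be the per-dosing probability of the event, the same on active and placebo (inert drug) and in every period.

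**Independent periods.**
- Placebo, one dosing: p.
- Overall active, three dosings: 1 − (1 − p)³.
- Ratio: 3 − 3p + p².
- The ratio equals 2 when p² − 3p + 1 = 0, so p = (3 − √5)/2 = 0.382. It exceeds 2 only below that value.

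**Correlated periods.** Under a beta-binomial model with within-person correlation ICC, put a = p(1 − ICC)/ICC and b = (1 − p)(1 − ICC)/ICC. The chance of no event in three dosings is b(b+1)(b+2) / [(a+b)(a+b+1)(a+b+2)]. For p = 20% and ICC 0.2, a = 0.8 and b = 3.2. That chance is 3.2 × 4.2 × 5.2 / (4 × 5 × 6) = 0.582, so the ratio is 0.418/0.20 = 2.09.

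| p (placebo) | Overall active, independent | Ratio, independent | Ratio, ICC 0.2 | Ratio, ICC 0.3 | Ratio, ICC 0.5 |
|---|---|---|---|---|---|
| 5% | 14.3% | 2.85 | 2.37 | 2.16 | 1.78 |
| 10% | 27.1% | 2.71 | 2.27 | 2.08 | 1.74 |
| 20% | 48.8% | 2.44 | 2.09 | 1.93 | 1.64 |
| 30% | 65.7% | 2.19 | 1.91 | 1.79 | 1.55 |
| 40% | 78.4% | 1.96 | 1.75 | 1.65 | 1.46 |
| 50% | 87.5% | 1.75 | 1.60 | 1.52 | 1.38 |
| 60% | 93.6% | 1.56 | 1.46 | 1.40 | 1.29 |

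The true ratio is 1 in every row. With correlation, the ratio drops to 2 at p of about 25% (ICC 0.2) or 15% (ICC 0.3). At ICC 0.5 it never reaches 2.

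**Event counts.** Expected events are proportional to dosing windows: 24/8 = 3, whatever the correlation, with equal windows. Window length may vary between periods, because protocol 1.1, 2.1 and 4.1 give dosing gaps of about two weeks, 14 days and at least one week. The 3-fold figure survives that if participants within a period share the same window, since every period contributes 6 active and 2 placebo.

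**Check of the remedy.** Per participant-period, expected incidence for an inert drug is 24p/24 = p on active and 8p/8 = p on placebo. The ratio is 1.0 for any p and any ICC.

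**The case against.** - **The like-for-like comparison is already in the table.** Each active treatment column (6 planned participants) covers one dosing per person, as does each placebo column. This stands. A reader might infer that the whole Part A TEAE table is biased, but the documents support that only for the aggregate column.
- **No active-versus-placebo contrast is planned.** SAP 9.4.3 rules out formal testing, no risk ratio is specified, and how many of 8 people ever had an event on drug is a legitimate description. This also stands. But in a descriptive analysis the table is the result, and this column sits beside placebo without a warning.
- **The denominator of 8 is inferred.** SAP 9.1.3 and 17.1.1 speak of exposure and counting within or per treatment, and do not say how the active treatments combine. SAP 9.5 provides no table shells. Eight is the natural reading, not a stated one, which is a further reason to define the column.
- **Noise will swamp the bias.** At p = 10%, a placebo column of 2 shows no events with probability 0.9² = 81%, and a column of 4 with probability 0.9⁴ = 66%. The ratios above are ratios of expected values, not predictions of the observed table.
- **The information is recoverable and no decision rests on it.** Numbers dosed per period are reported (SAP 11.0) and all AEs are listed. Protocol 6.6.1 bases escalation on data by dose level. A reader might infer that dose decisions would be distorted; nothing in the documents supports that.

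**Conclusion.** The point holds for one column. In Part A the overall active percentage accumulates three dosings per participant against one for any placebo figure, and for an inert drug it would be expected to be the higher of the two.

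The size depends on assumptions that the documents cannot settle. It is about 2 to 3 times placebo when the per-dosing risk is below about 38% and periods are roughly independent. It is about 1.5 to 2 times for commoner events or with strong within-person correlation, and lower still where both apply (1.38 at p = 50% with ICC 0.5). A reader might infer that an inert drug would always appear to more than double incidence. That does not follow, because it needs both the low risk and the near-independence. Many single SOC or PT rows probably have low risk, where the inflation is largest, but that too is an assumption.

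Part B is unaffected because each participant there takes only drug or only placebo. Table 12.3.1.6 is specified by study part and treatment, with no aggregate column. This is worth correcting because it is cheap and prevents a predictable misreading; it does not threaten the trial's conclusions.

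**What to change.** Add to SAP 17.1.1, for Part A Tables 12.3.1.4 and 12.3.1.5:

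- Report overall active and a pooled placebo column per participant-period: participant-periods with at least one event, over participant-periods dosed (planned 24 and 8).
- Report events per participant-period alongside the raw counts.
- If the participant-level overall active percentage is kept, footnote that it covers up to three dosings per participant and is not comparable with the placebo columns.

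The pooled placebo column would also supply the combined summary described in protocol 9.4.1. The cost is a short addition to the SAP, a changed denominator and one added column, with no new data and no protocol change. The small downside is that participant-periods within a person are not independent, which is acceptable in a descriptive table without confidence intervals or tests.

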6.3.2. Selection and Timing of Doses

All doses of the study intervention will be administered at the CRU approximately between 0800 hours and 1100 hours.

A trained CRU personnel member will administer all doses of the study intervention at the CRU.

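### Part A adverse events with no start date are counted as treatment-emergent but enter no treatment column, and a dosing-day event with no start time is given two conflicting start times

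*SAP*

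**What the plan says.** SAP 17.1.1 lists rules for incomplete adverse event (AE) records. They serve calculation only, and the imputed values are not to be shown.

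- **Missing start date.** The event is taken to follow treatment, so it is a treatment-emergent AE (TEAE). It is assigned to treatment in a single-treatment study, but "will not be attributed to treatment in studies with multiple treatments".
- **Missing start time, onset and duration.** "Missing AE start and/or end times for the calculation of onset and duration will be assumed to be at 00:01 for a start time", with 23:59 for a missing end time.
- **Missing start time, treatment assignment.** The event "will be assumed to occur after treatment on the recorded date one minute after dosing".
- **Missing severity or relationship.** "Missing AE severity or relationship will be assumed to be severe or related, respectively".

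The same section assigns a Part A TEAE that arises between two doses to the period of the earlier dose. The class-and-term tables have a column for each treatment, for overall active and for overall, within each study part. The severity and relationship table is specified by study part and treatment only. SAP 9.1.3 bases percentages on participants exposed within a treatment. Protocol 6.3.2 gives the clock time of dosing: "All doses of the study intervention will be administered at the CRU approximately between 0800 hours and 1100 hours".

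**The concern.** AEs and SAEs are the endpoints of the secondary safety objective in both parts, and the by-treatment tables are where a reader will compare doses, meal conditions and placebo. A rule that makes an event emergent but gives it no treatment leaves the columns unable to add up to the total. It also sits badly beside the worst-case rule for severity and relationship: an event missing both its date and its causality would be counted as related to study drug yet appear under no treatment.

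The two start-time rules conflict in a smaller way. One record can be assigned to a dose as starting just after it, while its derived onset falls hours before that dose.

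**Working it through.** **1. Does the multiple-treatment branch apply?** The Part A sequence table (SAP 6.0) has four sequences of two participants over four periods. Each sequence has placebo once and active drug three times, so each participant takes four different treatments. SAP 9.2.2 lists seven Part A treatment labels. The SAP does not name Part A as a multiple-treatment study, but no other reading fits. How the rule works in Part B, with one treatment per participant, is not stated.

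**2. Where does an undated Part A TEAE go?**

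| Output | Effect |
|---|---|
| Treatment columns, class-and-term tables | adds 0 |
| Overall-active column | not stated |
| Overall column | may count; not stated |
| Severity and relationship table | no overall column specified, so may be absent |
| AE listing | present |

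**3. Size in a column.** Exposed participants, from the sequence table and the placebo pooling in SAP 9.1.4:

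- each active condition: 3 sequences × 2 = 6, so one participant is 1/6 = 17%
- fasted placebo, Periods 1 and 2 pooled: 2 + 2 = 4, so 1/4 = 25%
- each fed placebo condition: 2, so 1/2 = 50%

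These apply to the participant percentage only if that person has no other event in the same class or term under that treatment, because participants are counted once. The event count falls by one in any case.

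**4. Onset of a dosing-day event with no start time.** Onset relative to dose = 00:01 minus dose time.

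- 08:00 dose: −7 h 59 min
- 11:00 dose: −10 h 59 min

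The assignment rule puts the same event at +1 min, so the two imputed starts differ by 8 h to 11 h. The negative value arises if onset is measured from that day's dose, which the SAP does not define.

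**5. Duration when both times are missing and the event ends the same day.**

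- Onset rule: 23:59 − 00:01 = 23 h 58 min
- Assignment time, 08:00 dose: 23:59 − 08:01 = 15 h 58 min
- Assignment time, 11:00 dose: 23:59 − 11:01 = 12 h 58 min

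The ratio is 1.50 to 1.85.

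**6. Can the period be recovered?** Protocol Table 1 collects AEs on Day -1 and on Days 1 to 5 of each period, and at follow-up. The visit of first report therefore bounds the onset from above and identifies the last dose before it.

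**The case against.** The strongest defence is that these are rules of last resort. SAP 8.2 already sends values needing investigation to data management, participants are confined from Day -1 to Day 3, and a site could usually supply at least a partial date. Leaving a truly unknowable assignment blank is defensible. On timing, the 00:01 and 23:59 pair gives the longest possible duration, which is a cautious convention, and dose plus one minute is also only an assumption. The planned AE tables concern class, term, treatment, relationship and severity; none is titled for onset or duration.

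Much of this stands and limits the point. Four stronger readings are tempting but not supported:

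- **That undated events vanish from the report.** All AEs are listed, SAEs and AEs leading to discontinuation are listed separately, and the overall column remains open to them.
- **That the SAP removes them from overall active.** It does not say how that column is derived.
- **That the rule favours active drug.** It removes placebo events in the same way. Active drug fills 24 of 32 planned participant-periods, so more undated events might fall there, but no difference in direction between conditions is shown.
- **That the tables will show pre-dose onsets or inflated durations.** At most the listing could carry such derived values, and the true start is unknown.

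The defence does not answer two things. When an event stays undated after query, its first report still usually identifies the dose, and the SAP discards that information. And two start times for one record are a contradiction, however cautious each is alone.

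**Conclusion.** The point holds as a minor one. If a Part A AE has no start date, SAP 17.1.1 counts it as treatment-emergent and gives it no treatment. The column for the treatment actually taken is then understated by 17, 25 or 50 percentage points per affected participant, for an active, fasted placebo or fed placebo condition. This assumes full cohorts as planned and no other event for that person in the same class or term under that treatment. The documents give no frequency for undated events, and they should be rare.

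The start-time conflict is about 8 to 11 h in onset for doses within the approximate 08:00 to 11:00 window. For a same-day event with both times missing, the duration is 23 h 58 min where the SAP's own assignment time would give about 13 to 16 h. It concerns only AEs dated on a dosing day and does not change the planned AE tables, whose treatment assignment already uses dose plus one minute.

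**What to change.** Amend SAP 17.1.1 in two places.

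1. After data query, attribute a Part A AE with a missing start date to the treatment of the last dose given before the visit at which it was first reported. A report on Day -1 or predose then goes to the preceding period, in line with the SAP's own between-period rule. Count the event in the overall column and, if that dose was active, in overall active. Show any TEAE that still cannot be attributed in the overall column with a footnote. Do not default such events to the most recent active treatment: that needs the report date, which would already identify the period, and it would move placebo events to active drug by rule.
2. For an AE dated on a dosing day with a missing start time, use dose time plus one minute for onset and duration as well as for treatment assignment, unless the record shows that it began before the dose.

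The cost is two sentences and a small programming change, with no new data and no change to conduct. SAP 3.0 requires an approved SAP before database lock and unblinding, so the rule should be fixed before then and not chosen once treatments are known.
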